2.2. Secondary Aim

To assess the feasibility of an inpatient ACP intervention, as well as the preliminary efficacy of the intervention on completion of advance directives (e.g., MOLST form, healthcare proxy form) and on EOL care (e.g., intensive care unit admissions, life-sustaining treatments, readmission rates, hospice enrollment, inpatient death).

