2.3. Hypothesis

An inpatient ACP intervention delivered by APPs and hematology/oncology fellows will improve completion of advance directives and EOL care.

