7.0. Treatment Protocol

7.1. Study Outline

For Aim 1, we will identify all inpatient APPs. We will email the intervention materials to them before the focus group meetings. Following this, the study team will conduct in-person or zoom/phone focus group interviews with APPs for 30-60 minutes. First, we will explain the rationale of the study. Second, we elicit preferences and feedback regarding the inpatient APP-delivered ACP intervention. This will include preferences on SICG training (i.e., length of training, in-person vs. virtual, live vs. prerecorded) and on SICG implementation (i.e., organization and content of the SICG including language that should be added, removed, or changed, workflow).

For Aim 2, we will screen and consent eligible patients of treating physicians at WCI. After consent, the study subject and caregiver (if applicable) will complete demographics and baseline measures. The patient will be provided with the “Patient Preparation Letter” following completion of baseline measures and prior to the inpatient ACP visit. This will allow the patient to review the document and prepare for their discussion with the APP/hematology/oncology fellow. Following this and during the same hospital admission, an inpatient ACP visit will be scheduled with an APP/hematology/oncology fellow on the inpatient malignant hematology service. The APP/hematology/oncology fellow will use the “Serious Illness Care Guide” during this visit with the patient. The APPs who participated in Aim 1 of this study have already completed training on how to use this guide. For additional APPs who may join in Aim 2 and hematology/oncology fellows who will join in Aim 2, they will complete the same training session as the original group of APPs on how to use this guide. Finally, at the end of the visit, the patient will be provided with the “Family Guide” (either from the APP/hematology/oncology fellow or the study coordinator). The patient can use this guide to help communicate with their family about the visit that they had with the APP/hematology/oncology fellow. The APP/hematology/oncology fellow will be able to access with the Epic Serious Illness Conversation Template on Epic and will document their conversation with the patient using the template in the electronic medical record.

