7.2.2. Clinical and Cancer Characteristics (Patient)

ECOG performance status, comorbidities, medications, weight, height, BMI, diagnosis and date of diagnosis, prior hematologic malignancies, stage/risk group, and treatment regimen will be abstracted from the medical records. This information will only be collected at baseline.

In addition, we will collect the following from the medical records (up to 5 years following their participation in the study or death) which will provide end of life quality indicators. We have previously collected this information in a retrospective fashion and will use similar procedures to extract this information prospectively from the medical records.

- Hospice enrollment (and timing relative to death)
- Palliative care referral (and timing relative to diagnosis)
- Chemotherapy administration within the last 2 weeks of life
- Completion of advance directives which include MOLST forms, living will, durable power of attorney for healthcare, and healthcare proxy forms (and timing related to diagnosis and death)
- Do not resuscitate order /Do not intubate order (and timing related to diagnosis and death)
- Emergency department visits in the last 30 days of life
- ICU admissions in the last 30 days of life
- Hospitalization in the last 30 days of life (number of hospitalizations, reasons for hospitalizations)
- Use of life-sustaining treatments (e.g., mechanical ventilation, vasopressors,

- tracheostomy, dialysis for acute kidney injury, percutaneous endoscopic gastrostomy) in the last 30 days of life
- Transfusion in the last 7 days of life
- Place of death (home, hospital, facility, etc.)
- Inpatient mortality rate

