7.2.3.7. Disease Understanding (Patient) – baseline and post-intervention – Aim 2

Disease Understanding – Patient: A questionnaire assessing patient's prognostic understanding of illness. They will also be asked if prognostic information was provided.

7.2.3.8. ACP Engagement Survey (Patient) – baseline and post-intervention – Aim 2

ACP Engagement Survey: 15-item engagement survey that assess patient self-efficacy and readiness for identification of a medical decision maker, identification of personal values, and flexibility in decision making and communication with their physician.

7.2.3.9. ACP Documentation – baseline and post intervention – Aim 2

Data on ACP documentation will be collected through the electronic medical record. This will include explicit statement of the patient's medical preferences for EOL care in a note, scanned MOLST form that was completed with their clinician, and/or scanned healthcare proxy form that was completed with their clinician.

7.2.3.10. Acceptability Questionnaire (Patient and APP/Fellow) – post-intervention only – Aim 2

Patient Acceptability Questionnaire (Aim 2): A questionnaire used in the original

Version Date: 5/10/23

PRMC#: UOCPC22039

Study Protocol

ClickIRB #: STUDY00007403

evaluation of the SICP implementation to assess the impact of the serious illness conversation on the patient's understanding and perception of their diagnosis.²⁸

Clinician Confidence Questionnaire (Aim 2): A questionnaire used in the original study evaluating the SICP implementation to assess clinician's self-perceived ability to implement the SICP in real practice. This will be used in Aim 2 at 3 time points: before the SICP training (led by [name]), after the SICP training, and at completion of the study (APPs and hematology/oncology fellows will complete the same training).²⁷

Clinician Acceptability Questionnaire (Aim 2): A questionnaire used in the original study evaluating the SICP implementation to assess the clinicians experience in using the SICP with patients.²⁷

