9.0 Data Management

9.1. Data Collection Table

9.1.1. Aim 1

a) APP

	Eligibility and consent form	Baseline Assessment	Post-Interview Assessment
Informed Consent	X		
Demographics		X	
Focus Group Interview		X	

9.1.2. Aim 2

a) APP/Hematology/Oncology Fellow

	Eligibility and consent form	Baseline Assessment	Post-Intervention Assessment
Informed Consent	X		
Demographics		X	
Qualitative Interview			X (at the end of the study)
Clinician Acceptability Questionnaire			X
Clinician Confidence Questionnaire		X (before and after SICP training)	X (at the end of the study)

b) Patient

Version Date: 5/10/23

PRMC#: UOCPC22039

Study Protocol

ClickIRB #: STUDY00007403

	Eligibility and consent form	Baseline Assessment	Post-Intervention Assessment
Informed Consent	X		
Demographics		X	
Clinical and Cancer Characteristics		X	
Cancer Health Literacy (CHLT-6)		X	
Disease Understanding		X	X
Activities of Daily Living (ADL), Instrumental Activities of Daily Living (IADL), Fall History		X	
Nutritional Status		X	
Geriatric Depression Scale-15		X	
Mini-Cog		X	
ACP Engagement Survey		X	X
Qualitative Interview			X
Patient Acceptability Questionnaire			X
End-of-Life Quality Indicators			X (up to 5 years or death; EMR)

c) Caregiver (if applicable)

	Eligibility and consent form	Baseline Assessment	Post-Intervention Assessment
Informed Consent	X		
Demographics		X	
Qualitative Interview			X
Acceptability Questionnaire			X

9.2. All hardcopy research records will be stored onsite in the URMC, in locked research files at the Wilmot Cancer Institute (WCI). The Cancer Center is secured with electronic key cards. Offices within the Cancer Center are again secured by key and data is kept in locked file cabinets. Electronic research records are stored on the URMC's password secured and firewall

Version Date: 5/10/23

PRMC#: UOCPC22039

Study Protocol

ClickIRB #: STUDY00007403

protected networks. These are the same methods of security used for patient medical records. For audio-recordings, these will be uploaded to Box within a week of the interview and deleted from the audio recorder. All study data will be kept for a period of 7 years after the study and all reports and publications are complete.

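### Do two different lists of advance-care documents, and a row missing from the patient table, leave the advance-directive outcome undefined?

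*Combined protocol and SAP*

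**What the plan says.** Section 2.2 sets out to assess the "preliminary efficacy of the intervention on completion of advance directives (e.g., MOLST form, healthcare proxy form", among other outcomes. Section 2.3 predicts that the intervention "will improve completion of advance directives and EOL care".

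Two sections bear on this outcome:

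- Section 7.2.2 lists, among the end-of-life quality indicators, "Completion of advance directives which include MOLST forms, living will, durable power of attorney for healthcare, and healthcare proxy forms". Timing is recorded relative to diagnosis and death, and records are followed for up to 5 years or until death.
- Section 7.2.3.9 is headed "ACP Documentation – baseline and post intervention". From the electronic record it takes a note stating end-of-life preferences and a "scanned MOLST form that was completed with their clinician, and/or scanned healthcare proxy form that was completed with their clinician".

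Patient table 9.1.2(b) has no row for ACP documentation. Its End-of-Life Quality Indicators row has a single mark, in the post-intervention column: "X (up to 5 years or death; EMR)". Section 8.2.2 describes all measures with summary statistics. For AML and MDS only, it compares the end-of-life indicators with a historical cohort.

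**The concern.** Directive completion is one of the two outcomes in the hypothesis, and the two lists can classify the same patient differently. A living will alone appears only in 7.2.2. A preference note alone appears only in 7.2.3.9. That note could come from the study visit itself, because section 7.1 says the clinician "will document their conversation with the patient using the template in the electronic medical record". A proxy form completed at home might also be treated differently. Section 7.1 gives patients a Family Guide and says "The patient can use this guide to help communicate with their family about the visit", so later family discussion is expected.

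If nothing says which list answers the hypothesis, the choice could be made after both results are known. If staff followed only the table, directives would be recorded after the visit without a baseline. Forms already on file would then be counted with forms that the visit prompted.

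**Working it through.** **The plan's own figures.** The plan gives no rate, target or sample size for directives. Its only related figures are the exact intervals for feasibility in 8.2.2, with n = 50. Recomputed, 25/50 gives 0.355 to 0.645 (width 0.29, half-width 0.145), against the plan's 0.36 to 0.65. For 35/50 the result is 0.554 to 0.821, which agrees with the printed limits. The printed width of 0.24 does not (0.821 − 0.554 = 0.267), but that is a separate matter.

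**The two lists side by side.**

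| Item | 7.2.2 | 7.2.3.9 |
|---|---|---|
| MOLST | yes | yes (scanned, with clinician) |
| Healthcare proxy | yes | yes (scanned, with clinician) |
| Living will | yes | not listed |
| Durable power of attorney | yes | not listed |
| End-of-life preference note | not listed | yes |
| Timing | relative to diagnosis and death; up to 5 years | baseline and post-intervention |

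The two shared items are the two that section 2.2 names as examples. Sections 2.2, 2.3 and 7.2.2 all speak of completing advance directives; 7.2.3.9 speaks of ACP documentation. On wording, 7.2.2 is the natural match to the hypothesis, and 7.2.3.9 is a short-term before-and-after measure.

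**The table.** Section 7.2.2 promises no baseline for directives, so the post-only End-of-Life row agrees with it. The only gap is the absent ACP documentation row. Other rows are absent too: Social Support (7.2.3.3) from the patient table, and the Geriatric Depression Scale for caregivers (7.2.3.4) from the caregiver table. This is a pattern of incomplete tables. It does not set up a rival schedule, and the 7.2.3.9 heading states both time points.

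**Whether baseline can be recovered.** Section 7.2.2 collects the date of diagnosis and the timing of forms relative to it. Section 5.1.7.g records the date of the baseline visit. Date of form = date of diagnosis + recorded interval. A form dated before the baseline visit was already there.

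**Size if the definition mattered.** Moving k patients shifts a combined rate by k/50: 2, 10, 14 and 20 points for k = 1, 5, 7 and 10. Seven patients is about the half-width above. These k are assumptions, all differences are taken to run one way, and a combined rate is needed, which the plan does not define. Reported item by item, MOLST and proxy differ only through the scanned-and-with-clinician wording.

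**Size if only the post-visit rate were reported.** Assume that 20% of patients lacking a form gain one, and let b be the share with a form at baseline. Post-only rate = b + 0.2(1 − b). Existing forms = 50b. New forms = 50 × 0.2(1 − b).

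| b | Post-only rate | Existing | New |
|---|---|---|---|
| 0 | 20% | 0 | 10 |
| 0.2 | 36% | 10 | 8 |
| 0.4 | 52% | 20 | 6 |
| 0.6 | 68% | 30 | 4 |
| 0.8 | 84% | 40 | 2 |

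Existing forms outnumber new ones when b > 0.2(1 − b), that is b > 1/6. The documents give neither b nor the 20%, so the table shows what could happen if the 7.2.3.9 baseline were ignored. It does not show what the plan will produce.

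**The case for a change.** The strongest case for a change is that improvement needs a reference level, and the historical comparison covers only AML and MDS. Patients with myeloma, lymphoma and other diagnoses are eligible under 3.5. For them the 7.2.3.9 baseline is the only reference, and that is the row the table omits. The study visit's template note could also meet 7.2.3.9 with no directive completed, and the repair would cost a few lines.

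Part of this stands. The lists differ, 8.2.2 does not link either one to the hypothesis, and the row is missing. The rest is weaker. The baseline for all diagnoses is stated in the 7.2.3.9 heading and remains readable from the record afterwards, so an omitted table row loses no data. The template note would matter if note and forms were merged into one score, which the plan does not do. As separate lines, the note cannot pass for a directive. A count of new forms follows from the baseline and post-intervention data already planned. The proxy form completed without a clinician is a possibility that the Family Guide wording does not establish. Scope for choosing between results is small where both measures are to be described and neither carries a test or threshold.

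**Conclusion.** No change to the plan follows. This is an unstated cross-reference between two overlapping measures together with a clerical omission from a table, and an analyst can fill both sensibly. Followed as written, the plan collects both measures and describes both. The study is a 50-patient single-arm pilot of preliminary efficacy. Its only benchmark is retention above 70%, which does not involve directives.

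The size of any effect on a reported rate cannot be derived from the documents, and it may be zero. The conclusion rests on three assumptions: forms in the electronic record carry usable dates, staff collect the baseline that 7.2.3.9 states or recover it from those dates, and document types are reported separately. It would weaken if the authors merged notes and forms into one score, or reported only a post-visit rate as evidence of improvement. The plan calls for neither.

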7.2.3.11. Feasibility metrics

Feasibility metrics will be collected:

- Retention rate (percentage of patients consented to the study ultimately completing all study components) – primary metric
- Recruitment rate (percentage of patients who are approached and agree to enroll) will also be described.

8.0. Data Handling and Statistical Considerations

8.1. Data Handling

8.1.1. The same protocols and procedures for data quality and control that are readily used for the NCI Community Oncology Research Program (NCORP) Research Base protocols currently being overseen by our office (which have accrued over 1,000 patients in the previous year) will be used for this study. Patients will fill out forms generated from RedCap and this information will be entered into RedCap (Section 9.5). They may also complete RedCap survey directly. Study personnel will perform Mini-Cog and the scores will be entered into RedCap.

8.1.2. It is anticipated that allowing for the appropriate number of evaluable participants and by checking self-report measures for completeness, we will have a full complement of data. Every effort will be made to encourage and facilitate participants' completion of all questionnaires and all items on the questionnaires for each study assessment. In the event that missing data occur, every effort will be made to contact participants via phone and obtain the data or to find out why the questionnaires or items are missing. The reasons for missing data will be documented. Missing questionnaire items will be treated in accordance with the documented scoring procedures. Although it is very unlikely that missing values will not occur randomly, we will confirm their randomness. Multiple imputation²⁹ will be

applied to (1) give more accurate statistical tests and standard errors for key treatment effect parameters and to (2) give some indication of the sensitivity of the analyses to missing data. The causes and pattern of the missing data will be examined and taken into consideration in the design of future studies.

8.1.3. For audio-recordings, these will be uploaded to Box within a week of the interview/clinic visits and deleted from the digital audio recorder (Sony). The recordings will be transcribed by a professional transcription service, and the transcripts will be used for data analysis.

8.1.4. Data collected (both assessments and transcripts) will only be accessed by the following: 1) The research team and 2) The treating physician (only if the patient consents for research information to be shared or if their treating physician is a study co- investigator).

8.2 Data Analysis and Sample Size:

8.2.1 Analysis Plan for Aim 1

Qualitative analyses: We anticipate thematic saturation will be reached with this number (N=approximately 10-15) of participants based on previous studies (i.e., the point at which no new data emerge).^{16,17} All interviews will be conducted and audio-recorded by study personnel and then transcribed by a professional transcription service. Two trained personnel (“coders”) will extract and highlight themes from the transcripts. We will analyze the qualitative data using grounded theory and constant comparative methods, with coding to structure data into categories and create groups according to the broader issues or themes.³¹ The themes will focus on feedback on training materials (e.g., prerecorded vs. interactive sessions, duration of training) and processes (e.g., workflow, template to document ACP visit in the electronic medical record) in the inpatient setting. These interviews will be audio-recorded by study personnel and then transcribed. We will keep an audit trail to establish trustworthiness. We will critically examine the data collection and analysis process, discuss emerging codes, and reach consensus on principal themes. These themes will be used to adapt the inpatient APP/fellow-delivered ACP intervention.

[figure not shown]
8.2.2 Analysis Plan for Aim 2

Quantitative analyses: We will use descriptive statistics to summarize feasibility metrics and all measures. Feasibility will be defined based on the retention rate (% of patients approached who consented and complete the ACP visit); >70% will be considered a successful benchmark for feasibility. Rates will be presented with associated two-sided 95% exact binomial confidence

intervals. A sample size of 50 patients produces a confidence interval with a maximum width of 0.29 (limits 0.36-0.65), when the observed feasibility rate is 0.50. We anticipate a higher feasibility rate, which will result in a narrower confidence interval. If the observed feasibility rate is 0.70, the width of the confidence interval is reduced to 0.24 (limits 0.55-0.82). If more than 50 patients are approached, then the confidence intervals will become narrower. Recruitment rate will be the % of patients approached who agree to participate (i.e., consent), and will be described similarly.

Models for comparison with historical control: For AML and MDS specifically, we will compare outcomes (EOL quality indicators) to a historical control cohort, which we have previously collected and published.¹² Rates of EOL outcomes in the historical cohort are shown in Figure 4, and range from <20% (chemotherapy in the last 14 days of life) to >80% (hospitalization in the last 30 days of life). Rates of EOL outcomes in this study population will be graphically summarized in a similar fashion. We aim to compare EOL outcome measures in this study population to EOL outcomes seen in the historical cohort referenced above.

Figure 1: End of life quality indicators (2014-2019)

Version Date: 5/10/23

PRMC#: UOCPC22039

Study Protocol

ClickIRB #: STUDY00007403

Qualitative analyses: All inpatient ACP visits and interviews will be audio-recorded by study personnel and then transcribed by a professional transcription service. Inpatient ACP visit transcript themes will focus on the APPs/hematology/oncology fellows ability to assess EOL concerns brought up by the patient and caregiver, as well as advance directive completion. Post-intervention interview themes will focus on participant experience during the inpatient ACP visit and feedback which will be used to further optimize the study procedures and intervention.

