3.3. Study Population

Aim 1 (completed): We will discuss the study at APP meetings and solicit interest in participation. [name] will serve as the APP lead and has preliminarily solicited support from APPs on the inpatient hematology service. We will approach APPs in person or via email communications. We will conduct focus group interviews to obtain feedback on training materials (e.g., prerecorded vs. interactive sessions, duration of training) and processes (e.g., workflow, template to document ACP visit in the electronic medical record) in the inpatient setting. Interviews will be audio-recorded by study personnel and then transcribed. Two trained personnel (“coders”) will extract and highlight themes from the transcripts. We anticipate up to 15 APPs will participate in this aim.

Version Date: 5/10/23

PRMC#: UOCPC22039

Study Protocol

ClickIRB #: STUDY00007403

Results from Aim 1 will be used to adapt the inpatient APP-delivered ACP intervention for use in Aim 2 (these will be shared with APPs via email prior to Aim 2 so they can review how their feedback was used to adapt the intervention). In other words, Aim 2 will occur after Aim 1 has been completed.

Aim 2: We will conduct a single arm study of 50 older patients, their caregivers (up to 2 caregivers per patient), and APPs/hematology/oncology fellows. We will approach all APPs on the inpatient hematologic malignancy service for Aim 2, with a goal of between 10-15 APPs participating. We will discuss the study at hematology/oncology fellow meetings and PIs ([name] [name] and [name]) will lead efforts to solicit support and involvement from fellows. We will approach all hematology/oncology fellows at Wilmot Cancer Institute for Aim 2, with a goal of between 10-12 fellows participating. We will consent up to 252 participants (75 patients, 150 caregivers, 15 APPs, 12 fellows) to account for screen fail or withdrawal with the target number being 50 patients and 100 caregivers.

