3.7. Number of Subjects

Aim 1: We plan to enroll APPs on the inpatient malignant hematology service. This phase will consist of focus group interviews with APPs. We plan to enroll up to 15 APPs. We will conduct at least two and up to four focus groups. We anticipate thematic saturation will be reached with this number of participants based on previous studies (i.e., the point at which no new data emerge).^{17,18}

Aim 2: We plan to enroll 50 patients total and their caregivers (up to 2 caregivers per patient if available) in 18 months. On average, 2-4 patients with hematologic malignancies are admitted to Wilmot Cancer Institute every day (and on average, the inpatient malignant hematology service cares for 15-25 patients daily). Our team has a proven track record in recruiting older patients with hematologic malignancies to supportive care and quality improvement studies (65-75% consent rate).^{17,18} Therefore, recruiting 50 patients and their caregivers [approximately 150 participants (50 patients; 100 caregivers), but can consent up to 225 patients/caregivers to account for screen fail/withdrawal; 75 patients and 150 caregivers] over 18 months is feasible. Patients and caregivers participation in this study will last approximately 4 weeks.

APPs who consent to the study in Aim 1 will also be consented to participate in Aim 2. APPs can also consent and join the study in Aim 2, after Aim 1 has been completed. Therefore, participation in Aim 1 of this study will last for 1 day for APPs and participation in Aim 2 of the study will last approximately 18 months for APPs. We plan to consent hematology/oncology fellows to participate in this study for Aim 2 only, since Aim 1 of this study has already been completed. Therefore, fellows will not participate in the focus group interviews. Participation in this study will last approximately 18 months for hematology/oncology fellows participating in Aim 2.

Version Date: 5/10/23

PRMC#: UOCPC22039

Study Protocol

ClickIRB #: STUDY00007403

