3.11. Vulnerable Subjects

Recruitment will exclude vulnerable populations such as fetuses, neonates, children, pregnant women, prisoners, and institutionalized individuals. We will also exclude adults who are deemed to not have decisional capacity and those who lost their consent capacity during the study period, as per their treating oncologist.

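### The retention rate that decides Aim 2 feasibility has two conflicting definitions, and the only benchmark (>70%) is tied to one of them

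*Combined protocol and SAP*

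**What the plan says.** Section 7.2.3.11 lists the feasibility metrics. The one marked as primary is "Retention rate (percentage of patients consented to the study ultimately completing all study components". It carries no threshold. Recruitment rate is listed separately, as the share of approached patients who enrol.

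Section 8.2.2 says feasibility will be judged on the "retention rate (% of patients approached who consented and complete the ACP visit); >70% will be considered a successful benchmark for feasibility". Its precision statement uses 50 patients and exact two-sided 95% intervals. At an observed rate of 0.70 it says "the width of the confidence interval is reduced to 0.24 (limits 0.55-0.82", and it adds: "If more than 50 patients are approached, then the confidence intervals will become narrower".

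Three other places bear on who is counted:

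- Section 3.3: "We will consent up to 252 participants (75 patients, 150 caregivers, 15 APPs, 12 fellows) to account for screen fail or withdrawal", against a target of 50 patients.
- Section 3.11 excludes "those who lost their consent capacity during the study period, as per their treating oncologist".
- Section 3.7: "Patients and caregivers participation in this study will last approximately 4 weeks". The chart follow-up of up to 5 years (sections 7.1 and 7.2.2) comes after that.

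No section reconciles the two definitions.

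**The concern.** One name covers two quantities. They differ in the numerator (every study component, or the ACP visit alone) and, on the plain reading of 8.2.2, in the denominator (consented, or approached). The approached version combines recruitment with retention, so it measures something other than what 7.2.3.11 describes.

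This is the only success benchmark in Aim 2. If the numerator and denominator can be settled after the data are in, the benchmark is not prespecified. The analysis is descriptive and no stopping rule depends on it, so what is at risk is the reported feasibility conclusion.

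**Working it through.** **1. The plan's precision figures.** Inputs from 8.2.2: n = 50, exact (Clopper-Pearson) 95% interval.

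| Observed | Exact limits | Width | Plan states |
|---|---|---|---|
| 25/50 = 0.50 | 0.355-0.645 | 0.289 | 0.36-0.65, width 0.29 |
| 35/50 = 0.70 | 0.554-0.821 | 0.267 | 0.55-0.82, width 0.24 |
| 40/50 = 0.80 | 0.663-0.900 | 0.237 | not given |

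The first width reproduces. At 0.70 the limits reproduce but the width does not: 0.82 - 0.55 = 0.27. A width of 0.24 belongs to an observed rate of 0.80.

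**2. The two definitions on the same data.** Let A = approached, C = consented, V = completed the ACP visit, F = completed all components. Section 8.2.2 is V/A; section 7.2.3.11 is F/C. The counts are illustrative assumptions, and the 70% benchmark is applied to both rates.

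| Case | A | C | V | F | V/A (8.2.2) | F/C (7.2.3.11) |
|---|---|---|---|---|---|---|
| a | 72 | 50 | 45 | 40 | 45/72 = 62.5%, not met | 40/50 = 80%, met |
| b | 67 | 50 | 48 | 34 | 48/67 = 71.6%, met | 34/50 = 68%, not met |

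Neither definition is always the stricter one.

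**3. The numerator alone.** Suppose 8.2.2 is read as the share of consenting patients who complete the visit. With C = 50, V = 45 and F = 34, the rates are 45/50 = 90% and 34/50 = 68%. They can differ because the post-intervention measures and the interview within 4 weeks follow the visit (section 7.1).

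**4. The ceiling on the approached denominator.** V/A = (C/A) × (V/C), so it cannot exceed the recruitment rate C/A. For an expected rate above 0.70, completion among consenters must exceed 0.70 / consent. Section 3.7 cites "supportive care and quality improvement studies (65-75% consent rate" for the team's earlier work; 80% and 90% are my extension.

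| Consent | Completion needed |
|---|---|
| 65% | 0.70/0.65 = 107.7%, impossible |
| 70% | 0.70/0.70 = 100%, and that gives exactly 70%, not more |
| 75% | 0.70/0.75 = 93.3% |
| 80% | 0.70/0.80 = 87.5% |
| 90% | 0.70/0.90 = 77.8% |

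To show the effect of the denominator alone, assume 80% of consenters complete and use the same completion count for both rates. The binomial chance of observing more than 70% is then:

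- 50 consented, at least 36 completers: 93.9%.
- 67 approached at 75% consent, success probability 0.60, at least 47: 5.6%.
- 72 approached at 70% consent, success probability 0.56, at least 51: 0.7%.
- 77 approached at 65% consent, success probability 0.52, at least 54: 0.1%.

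**5. Who is counted.** With 75 consented (the ceiling in 3.3) and 50 completers, the rate is 50/75 = 66.7%. If 10 of the 75 are screen failures and are removed (assumption), it is 50/65 = 76.9%. For loss of capacity, 34/50 = 68% becomes 34/48 = 70.8% if 2 such patients are removed (assumption). Each choice crosses 70%.

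**The case against.** Only 8.2.2 sets a threshold, so a literal reader has one decision rule, and judging the 7.2.3.11 rate against 70% borrows the benchmark from another section. That is accurate. But 7.2.3.11 calls its version primary and 8.2.2 bases feasibility on a rate of the same name, so a reader cannot tell which was meant.

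The denominator conflict is less certain than the numerator conflict. Fifty is the enrolment target. With any refusals more than 50 must be approached, so the n = 50 precision statement fits a consented denominator, and 8.2.2 already defines recruitment rate separately. Loose drafting is plausible. If that is the explanation, cases a and b and the whole of step 4 fall away. The sentence about approaching more than 50 points the other way, and step 3 stands regardless.

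The counts are constructed. Case b needs 14 of 48 patients to be lost after the visit, and the 65-75% consent rate is past experience, not a forecast. The figures show that the verdict can flip, not how often it would. Ten screen failures in 75 is also high, given no listed patient exclusion criteria (3.5) and an eligibility check before approach (4.1.2). The counting rules are secondary to the conflict itself.

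Finally, this is a descriptive pilot and both rates can be computed from data already collected. That limits the harm and makes the correction easy, but 8.2.2 still declares success at 70%.

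**Conclusion.** The concern holds and should be corrected before the feasibility result is reported. The numerator conflict is certain: it survives the most favourable reading of 8.2.2 and gives 90% against 68% in the illustrative case. The denominator conflict follows from the plain wording and the sentence on approached patients, though the use of 50 leaves some doubt. If the approached denominator is meant and consent falls at 65-70%, an expected rate above 70% is out of reach; at 75% consent it needs completion above 93.3%. Those figures rest on the consent range in 3.7 carrying over to this study.

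The 0.24 width is a minor slip beside correct limits. The weight of the point rests on the definitions alone.

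**What to change.** Put one definition in both 7.2.3.11 and 8.2.2 and tie the >70% benchmark to it.

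- **Denominator.** The simplest choice is the one already labelled primary: consented, eligible patients, with screen failures excluded and withdrawals, deaths and losses counted as non-completers. State how patients who lose consent capacity under 3.11 are counted.
- **Numerator.** Choose either the ACP visit or all patient components within the roughly 4-week participation, and report the other as a second rate on the same denominator. If all components is chosen, list them. Table 9.1.2(b) is the natural source, but it has no row for the ACP visit, so name the visit explicitly, and state that the later chart follow-up is outside.
- **Recruitment.** Keep consented/approached as the recruitment rate only. If the approached denominator is retained for feasibility, call it something other than retention and justify 70% against the expected consent rate.
- **Precision.** Correct the width at 0.70 from 0.24 to 0.27 and state precision for the chosen denominator. For 50 consented: 0.55-0.82 at 0.70 (width 0.27) and 0.66-0.90 at 0.80 (width 0.24). On an approached denominator near 0.70: 47/67 gives 0.577-0.807 (width 0.23) and 54/77 gives 0.586-0.800 (width 0.21).

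The cost is wording in two sections and one corrected number. No patients, visits or data are added. One of the two current rates becomes secondary.
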